## 1.0 OBJECTIVES / SPECIFIC AIMS

This study is funded through an administrative supplement to the parent SCORE grant (U54 DA016511, Pro# 00081360; PI: [name]), hereafter referred to as the “parent study.”

The primary objective of this supplement study is to collect pilot data to expand the relevance of Cannabis use disorder (CUD) to Alzheimer’s disease and related dementias (ADRD). We will recruit older adults ages 50-80 with CUD to undergo the proposed assessments in addition to ADRD-focused biomarkers (from MRI, blood, and neurocognitive testing) of ADRD risk.

**Specific Aim: Evaluate the associations between cognition, stress, endogenous progesterone, cannabis use, and biomarkers of ADRD risk, and whether sex plays a moderating role.** Consistent with the CUD literature in adulthood, we hypothesize that older adults with CUD will demonstrate normatively worse cognitive function. We will conduct preliminary analyses to examine whether this effect is greater in women than in men, hypothetically due to post-menopausal loss of progesterone and greater levels of stress driving cannabis use. We will examine the extent to which cognitive decrements are associated with ADRD biomarkers to generate subsequent hypotheses regarding the potential impact of cannabis use on ADRD risk.

## 2.0 BACKGROUND

**Cannabis use in aging and risk for cognitive decline.** Cannabis use among persons ages 50+ is rising. About 9.0% of adults ages 50-64 and 2.9% of adults ages 65+ have used cannabis in the past year (Han et al., 2018). Despite this trend, there is limited data on the impact of cannabis use in older adults (Briscoe et al., 2018). One particular risk of cannabis use for which older adults are especially vulnerable is cognitive decline. By mid-life an individual’s lifetime risk for Alzheimer’s disease and related dementias (ADRD) is 10-20% (Chene et al. 2015) and rises to where 1 in 3 older adults die of ADRD (Alzh Assn, 2019). Recent or heavy cannabis use may also increase risk for medical conditions such as vascular disease (Pacher et al., 2018), which, in turn, increase risk for ADRD (Kloppenborg et al., 2008) Thus, cannabis use may increase the incidence of cognitive decline and ADRD in older adulthood.

**Sex differences in ADRD and depression/stress.** While the incidence of ADRD is comparable between sexes, sex differences in risk factors may disproportionately elevate risk for women. Women are twice as likely to experience depression than men and mid-life depression confers as much as a 70% increased risk for ADRD. Thus, women may be at greater risk via a stress-mediated pathway (Mielke, 2018). This pathway may be especially relevant when investigating risk for ADRD within the context of cannabis use, as approximately one-third of older current cannabis users are women (Benitez et al., 2020).

**Stress in older cannabis-using women.** No prior research has verified whether sex differences in the role of stress on cannabis use motivations and craving extend to older adulthood. There is reason to believe that this stress-mediated pathway may differ in aging. The prevalence of depression decreases over the lifespan, and in older adulthood depression differs in risk factors, presentation, etiology, and prognosis depending on its onset (Fiske et al., 2009). That is, “late onset” depression is more likely to have vascular disease or incipient ADRD, whereas “early onset” depression is associated with significant family mental health history or predisposing traits. These variations may correspond to different patterns in cannabis use, motivations, or craving, and potentially to how cannabis ultimately exerts its effects.

**Progesterone and substance abuse.** The association between progesterone and substance abuse in post-menopausal women has not been studied, although these interactions are currently of great funding interest (Gipson & Bimonte-Nelson, 2020). Post-menopausal women may not have the benefit of

experiencing the stress-reducing effects of progesterone as this attenuates substance use, thereby potentially making them at disproportionately greater risk for substance use-related outcomes and ADRD.

### 3.0 STUDY ENDPOINTS

**Primary Outcome:** Global Cognitive Ability (GCA). Consistent with the CUD literature in adulthood (Sagar & Gruber, 2018), we hypothesize that older adults with CUD will demonstrate normatively worse cognitive function. The primary measure is the GCA factor (Kiselica et al., 2020). This is a psychometrically robust, factor analytically-derived (using 12 neurocognitive test scores), and demographically-normed (for age, sex, and years of education) index that yields a z-score representing global cognitive function.

*Planned analysis:* We will first conduct one-sample t-tests to determine whether this CUD sample's z-score mean is significantly below the normative population mean of z-score=0. We will then statistically test whether GCA is lower in women than in men, hypothetically due to post-menopausal loss of progesterone and greater levels of stress driving cannabis use. Next, we will assess the associations between GCA and progesterone measurements and stress (i.e. averaged pre- and post-cue CREMA session data and TSST cortisol and subjective ratings), by sex. Finally, we will examine the associations between GCA and ADRD biomarkers, by sex, to obtain preliminary estimates of potential associations between cognition and ADRD risk in the setting of CUD.

### 5.0 INCLUSION AND EXCLUSION CRITERIA/ STUDY POPULATION

#### Inclusion Criteria

- i. Age 50-80.
- ii. English as a first/primary language.
- iii. Functional visual and auditory acuity (aided or unaided) to complete tests.
- iv. Capacity to independently provide informed consent and function at an intellectual level sufficient to allow completion of all instruments.
- v. Currently meets DSM-5 criteria for CUD or uses cannabis at least 4 days per week.
- vi. Consent to abstain from alcohol and cannabis use for >12 hours prior to Study Visit (Day 0), and TSST (Day 8).
- vii. Consent to abstain from all drugs other than cannabis or nicotine for the duration of the study.

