#### Exclusion Criteria

- i. Meet DSM-5 criteria for moderate or severe alcohol or substance use disorder (other than nicotine or cannabis) within the last 12 months.
- ii. History of major neurocognitive disorder or developmental disorder per DSM-5.
- iii. A Telephone Interview for Cognitive Status (TICS) score of  $\leq 22$ .
- iv. Significant or unstable medical condition/s that impact cognition as deemed by study investigators, such as active significant cardiac, cerebrovascular, neoplastic, infectious, or metabolic disease, or longstanding and intractable severe mental illness (e.g. schizophrenia spectrum disorder, bipolar disorder).
- v. Daily use of medications that adversely impact cognition in aging (i.e. anticholinergics and sedatives).
- vi. Current suicidal or homicidal ideation/risk.
- vii. Unable to complete/comply with procedures or pose threat to research staff.
- viii. Standard MRI contraindications (e.g., implants, claustrophobia).
- ix. Women who are pregnant, nursing or of childbearing potential and not practicing an effective means of birth control.

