## 10.0 STUDY DESIGN / METHODS

Participants will complete 4 sets of procedures: Eligibility Assessment, Study Visit (Day 0), Cue Reactivity Ecological Momentary Assessment (CREMA; Days 1-7), and the Trier Social Stress Task (TSST; Day 8). *With the exception of the procedures within Study Visit 0, all of the procedures described here are IRB-approved for the parent study (Pro# 00081360):*

Procedure: **ELIGIBILITY ASSESSMENT**

Setting: Either or a combination of electronic/online platform or in-person delivery (at the Addiction Sciences research space at [name]), depending on participant preference  
 Personnel: Research staff  
 Duration: 1.5 hours  
 Description: Following consenting, trained research staff will administer the following semi-structured interviews and questionnaires to ascertain that he/she meets the clinical eligibility criteria using measures that are already approved and being administered in the parent study.  
 Measures: Clinical Assessments and Substance-Related Questionnaires

Mini-International Neuropsychiatric Interview (MINI)

Marijuana Use Questionnaire

Time Line Follow-back (TLFB)

Inventory of Drug-Taking Situations (IDTS)

Perceived Stress Scale (PSS)

Adverse Childhood Experiences (ACE) Questionnaire

Personal History (May be done at Eligibility Assessment or Day 0: Study Visit)

Subject Demographics, Medications, and Health History: All participants will complete 3 brief questionnaires from the National Alzheimer’s Coordinating Centers Uniform Dataset (NACC-UDS) to capture all relevant personal and medical history variables.

Geriatric Depression Scale: A 30-item self-report measure of depression severity.

Menstrual, Reproductive, and Hormone Therapy History: Female participants will complete a brief questionnaire based on the PhenX Toolkit. These measures were administered in NIH-funded lifespan studies including the Women’s Interview Study of Health and the Study of Women Across the Nation.

Mobile Device Proficiency Questionnaire-16 (Roque & Boot, 2018): This brief measure will index participants’ facility with mobile technology. Researchers will use this information to triage participants in need for more assistance with CREMA.

Procedure: **DAY 0: STUDY VISIT**

Setting: Center for Biomedical Imaging (CBI; [name]) and Research Nexus

Personnel:	Research staff
Duration:	1 hour (at CBI) and 2 hours (at Nexus)

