## 12.0 DATA MANAGEMENT

### **Specific Aim: Evaluate the associations between cognition, stress, endogenous progesterone, cannabis use, and biomarkers of ADRD risk, and whether sex plays a moderating role.**

Consistent with the CUD literature in adulthood (Sagar & Gruber, 2018), we hypothesize that older adults with CUD will demonstrate normatively worse cognitive function. The primary measure is the Global Cognitive Abilities factor (Kiselica et al., 2020). This is a psychometrically robust, factor analytically-derived (using 12 neurocognitive test scores), and demographically-normed (for age, sex, and years of education) index that yields a z-score representing global cognitive function. We will conduct one-sample t-tests to determine whether this CUD sample's z-score mean is significantly below the normative population mean of z-score=0.

We will conduct preliminary analyses to examine whether this effect is greater in women than in men, hypothetically due to post-menopausal loss of progesterone and greater levels of stress driving cannabis use. The measures of interest are the Global Cognitive Abilities factor z-score, baseline progesterone measurements, and stress (i.e. averaged pre- and post-cue CREMA session data and TSST cortisol and subjective ratings). First, we will conduct independent samples t-tests to determine whether the Global Cognitive Abilities factor z-score is different between sexes. Second, we will run analyses of covariance (covariate: age) to test differences in baseline progesterone between men and post-menopausal women (which should be absent per Oettel & Mukhopadhyay, 2004). Next, we will run Spearman's rank correlations to investigate associations between stress and Global Cognitive Abilities by sex. Should stress be a more salient feature among women with CUD, we would find an inverse correlation between CREMA session data and Global Cognitive Abilities in women.

We will examine the extent to which cognitive decrements are associated with ADRD biomarkers to generate subsequent hypotheses regarding the potential impact of cannabis use on ADRD risk. We will conduct Spearman's rank correlations between the Global Cognitive Abilities factor z-scores and ADRD biomarkers (with transformations, as appropriate), by sex, to obtain preliminary estimates of potential associations between cognition and ADRD risk in the setting of CUD.

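### The aims, hypothesis and primary GCA test are stated for adults with CUD, but inclusion v also admits frequent users without CUD

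*Combined protocol and SAP*

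**What the plan says.** Section 5.0, inclusion v, sets the cannabis criterion: "Currently meets DSM-5 criteria for CUD or uses cannabis at least 4 days per week".

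The other sections describe a narrower group:

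- Section 1.0, on recruitment: "We will recruit older adults ages 50-80 with CUD".
- Section 3.0, on the hypothesis: "we hypothesize that older adults with CUD will demonstrate normatively worse cognitive function". Sections 1.0 and 12.0 say the same.
- Section 3.0, on the primary analysis: "We will first conduct one-sample t-tests to determine whether this CUD sample" has a mean GCA z-score below the normative value of 0. Section 12.0 repeats this: "We will conduct one-sample t-tests to determine whether this CUD sample".
- Section 12.0, on the biomarker correlations: the purpose is "to obtain preliminary estimates of potential associations between cognition and ADRD risk in the setting of CUD".

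The only exclusion that concerns substance use disorder sets cannabis aside: "Meet DSM-5 criteria for moderate or severe alcohol or substance use disorder (other than nicotine or cannabis) within the last 12 months". Section 10.0 lists the MINI, the Marijuana Use Questionnaire and the TLFB at the Eligibility Assessment, used "to ascertain that he/she meets the clinical eligibility criteria". Section 6.0 sets a target of 50 completers, 25 of each sex, with no split by CUD status. The power paragraph in Section 12.0 says the pilot is meant to supply effect sizes for sizing later studies.

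**The concern.** The primary analysis asks whose mean GCA lies below the norm. The hypothesis answers that it is people with CUD; the entry rule answers that it is people with CUD together with frequent users who may not have it. If both passages are followed as they stand, the study enrols the wider group and reports it under the narrower name.

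This matters more than a loose label usually would, because effect sizes are a main product of this pilot. A later grant that took the GCA effect as a CUD effect could be planned for a population that was not the one measured. No planned output shows how many participants lack CUD, so a reader could not tell whether the label was harmless.

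**Working it through.** **1. Text comparison.**

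| Place | Group described |
|---|---|
| Section 1.0, recruitment and hypothesis | CUD |
| Section 3.0, hypothesis and primary t-test | CUD |
| Section 12.0, hypothesis, primary t-test, biomarker analysis | CUD |
| Section 5.0, inclusion v | CUD, or use on at least 4 days a week |

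Four things could reconcile these entries: an exclusion that removes frequent users without CUD, a definition of CUD that includes frequent use, a cap on their number, or an analysis restricted to, stratified by or adjusted for CUD status. None is in the documents.

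**2. No figure in the plan to reproduce.** The plan gives n = 50 but no alpha, power, effect size, SD or expected share without CUD. Everything below is an assumed illustration.

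**3. Size of the shift.** Let D be the CUD deficit, f the share without CUD, and r the non-CUD deficit as a multiple of D. With within-group SD 1:

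- full-sample mean = -D(1 - f + f·r)
- shift from the CUD mean = f × (non-CUD mean - CUD mean) = f·D·(1 - r)
- mixture SD = √(1 + f(1 - f)[D(1 - r)]²)

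Example with D = 0.40, f = 0.30, r = 0: mean = -0.40 × 0.70 = -0.28; SD = √(1 + 0.21 × 0.16) = 1.017; standardised effect = 0.28/1.017 = 0.275.

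The table gives the smallest N with at least 80% power for a later one-sample t-test (noncentral t) planned on the full-sample mean and mixture SD. Section 3.0 asks a directional question but states no sidedness, so both choices are shown.

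| f | r | Mean | N, two-sided 5% | N, one-sided 5% |
|---|---|---|---|---|
| 30% | 0 | -0.28 | 106 | 83 |
| 30% | 0.5 | -0.34 | 71 | 56 |
| 30% | 1 | -0.40 | 52 | 41 |
| 30% | 1.5 | -0.46 | 40 | 31 |
| 10% | 0 | -0.36 | 64 | 50 |
| 10% | 0.5 | -0.38 | 57 | 45 |
| 10% | 1 | -0.40 | 52 | 41 |
| 10% | 1.5 | -0.42 | 47 | 37 |

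The reference value is 52 (two-sided) or 41 (one-sided), where the groups do not differ. A departure from it is an error only if the later study enrols CUD alone. In that case, with a two-sided test, 40 participants would give 69% power, and 106 would be about twice the number needed (106/52 = 2.04). A later study with the same entry rule should use the full-sample figure.

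**4. Comparison with the pilot's own noise.** At n = 50 and SD 1, the 95% CI half-width for the mean is 2.010/√50 = 0.284. Around -0.40 the interval runs from -0.684 to -0.116. By the same two-sided method, those limits imply planned samples of 19 to about 586. The assumed shifts at f = 30% (0.06 to 0.12 in absolute value where r is not 1) are well inside that range.

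**5. Precision of a CUD-only repeat.** The half-width is t(0.975, n - 1)/√n with SD 1: 0.284 at n = 50, 0.300 at n = 45 (10% without CUD) and 0.344 at n = 35 (30% without CUD). At n = 50 and f = 30%, using the mixture SD raises 0.284 to at most 0.289.

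**The case against.** The case on the other side does not dispute the mismatch; it disputes its weight. Five points deserve an answer.

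- **No bias is shown.** The documents do not give the recruitment mix, and the bias could be zero. This stands. What is established is a conflict about the analysed population, not a known error in the estimate.
- **The illustration is small beside sampling error.** This stands too, as step 4 shows, and the sample sizes depend on the assumed sidedness. It limits the illustration. It does not reconcile the passages, and sampling error is expressed in a confidence interval while a mislabelled population is not.
- **CUD may be shorthand for regular use.** Possibly in part, since the Specific Aim also names cannabis use as a variable. But inclusion v itself treats the diagnosis and the frequency as separate routes. If shorthand was meant, rewording is still the remedy.
- **The data are already collected.** Largely accepted: the instruments are listed with no skip rule. The text still does not say that CUD is rated when frequency alone qualifies someone, and no analysis or table uses CUD status.
- **Matching wording and counts would be enough.** They would remove the contradiction. The CUD-only repeat is needed to support a CUD-specific conclusion, which is what the hypothesis now states.

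**Conclusion.** The concern holds. Inclusion v admits people without CUD, while the recruitment statement, the hypothesis and the primary test are worded for CUD, and nothing in the documents resolves the difference. This should be fixed. Confidence is high on the inconsistency itself.

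The effect on the result cannot be derived from the documents. It is nil if no non-CUD users enrol. If the two groups have equal mean GCA, the estimate is unbiased and only the label is wrong. Otherwise the shift equals the non-CUD share times the difference in means, and it may go either way. The figures of up to 0.12 in the mean, and 40 to 106 planned participants against 52, rest on the assumed deficit of 0.40, SD 1, 30% without CUD and a two-sided 5% test with 80% power.

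**What to change.** 1. In Sections 1.0, 3.0 and 12.0, describe the hypothesis and the analysed population in the terms of inclusion v: adults aged 50 to 80 with DSM-5 CUD or cannabis use on 4 or more days a week. Keep the full sample as the main analysis set.
2. In Section 10.0, state that DSM-5 CUD status is recorded at the Eligibility Assessment for every participant, including those who qualify on frequency. Report the numbers with and without CUD, by sex.
3. Pre-specify one CUD-only repeat of the primary one-sample GCA test. Base any CUD-specific conclusion, and any CUD effect size for GCA used in planning, on that repeat. Describe the sex, stress and biomarker results as applying to the full mixed sample; they need no CUD-only reruns.

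The cost is wording in three sections, one sentence in Section 10.0, one table of counts and one repeated t-test. It needs no new visit and probably no new instrument. The statistical price is lower precision in the repeat, as in step 5 of the working.

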#### Exclusion Criteria

- i. Meet DSM-5 criteria for moderate or severe alcohol or substance use disorder (other than nicotine or cannabis) within the last 12 months.
- ii. History of major neurocognitive disorder or developmental disorder per DSM-5.
- iii. A Telephone Interview for Cognitive Status (TICS) score of  $\leq 22$ .
- iv. Significant or unstable medical condition/s that impact cognition as deemed by study investigators, such as active significant cardiac, cerebrovascular, neoplastic, infectious, or metabolic disease, or longstanding and intractable severe mental illness (e.g. schizophrenia spectrum disorder, bipolar disorder).
- v. Daily use of medications that adversely impact cognition in aging (i.e. anticholinergics and sedatives).
- vi. Current suicidal or homicidal ideation/risk.
- vii. Unable to complete/comply with procedures or pose threat to research staff.
- viii. Standard MRI contraindications (e.g., implants, claustrophobia).
- ix. Women who are pregnant, nursing or of childbearing potential and not practicing an effective means of birth control.

## **6.0 NUMBER OF SUBJECTS**

Target completion is 50 participants, comprising men (n=25) and women (n=25).

## **7.0 SETTING**

Procedures will take place at the SCTR Research Nexus, Addiction Sciences research space at [name], and the research-dedicated Center for Biomedical Imaging 3T Siemens Prisma MRI at [name]. Certain procedures, such as consenting and questionnaire completion may be completed virtually through telehealth using an MUSC approved electronic platform (e.g. [musc.doxy.me](http://musc.doxy.me) or REDCap).

## **8.0 RECRUITMENT METHODS**

Potential Participants will be recruited via:

- Ongoing research studies by the study PI/Co-Investigators in which participants have consented to be contacted for other studies
- Direct referrals through MUSC Research staff
- Community recruitment by a member of the study team that is qualified and is delegated by the PI. Recruitment will be in both written and verbal format including but not limited to IRB approved printed and electronic materials. Participants will be recruited at community events as well as events marketed toward health and disease awareness.

Recruitment materials may include flyers, handouts, electronic and physical bulletin board postings, social media/message boards (i.e., Craigslist, MUSC Broadcast Research studies section of Yammer, Instagram, Facebook), web-based recruitment tools (e.g., ResearchMatch, Trial Match), newsletter/newspaper/media advertisements, and recruitment talks at local community events/organizations and surrounding community. Approvals will be obtained prior to displaying flyers in other community locations if/as needed.

### Pre-Screening and Screening

Individuals interested in participating will be screened either by telephone or in person by research staff and the study and its requirements will be briefly explained to them. If subjects verbalize interest in participating in the study, staff will explain the screening process and ask if they would be willing to participate in the screening.

If the potential Participant agrees to be screened, research staff will ask questions that focus on inclusion/exclusion psychiatric diagnoses, medical status, current medication regimen, and ability and willingness to fill out the necessary assessments and commit to completion of study procedures. Pre-screening will include the administration of the Telephone Interview for Cognitive Status (TICS). TICS is a brief telephone-based cognitive assessment frequently used in clinical trials, where a score of  $\leq 22$  is a validated cut-off to exclude potential participants with possible dementia (Manly et al., 2011).

If the potential Participant meets all inclusion/no exclusion criteria that can be assessed via subject report and TICS, he/she will be asked to consent to the full study.

